7 STUDY TREATMENTS

7.1 Method of Assigning Subjects to Treatment Groups

All subjects in this study will receive the treatment.

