The relationship of an AE to Synvisc-One should be assessed using the following the guidelines in Table 2.

Table 2. AE Relationship to Study Drug

| Relationship to Drug | Comment |
|-----------------------------|---|
| Definitely | Previously known toxicity of agent; or an event that follows a reasonable temporal sequence from administration of the drug; that follows a known or expected response pattern to the suspected drug; that is confirmed by stopping or reducing the dosage of the drug; and that is not explained by any other reasonable hypothesis. |
| Probably | An event that follows a reasonable temporal sequence from administration of the drug; that follows a known or expected response pattern to the suspected drug; that is confirmed by stopping or reducing the dosage of the drug; and that is unlikely to be explained by the known characteristics of the subject's clinical state or by other interventions. |
| Possibly | An event that follows a reasonable temporal sequence from administration of the drug; that follows a known or expected response pattern to that suspected drug; but that could readily have been produced by a number of other factors. |
| Unrelated | An event that can be determined with certainty to have no relationship to the study drug. |

Serious Adverse Experiences (SAE)

An SAE is defined as any AE occurring at any dose that results in any of the following outcomes:

- death

- a life-threatening adverse experience
- inpatient hospitalization or prolongation of existing hospitalization
- a persistent or significant disability/incapacity
- a congenital anomaly/birth defect

Other important medical events may also be considered an SAE when, based on appropriate medical judgment, they jeopardize the subject or require intervention to prevent one of the outcomes listed.

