10.1.1 Serious Adverse Experience Reporting

Study sites will document all SAEs that occur (whether or not related to study drug) per [UCSF CHR Guidelines](#). The collection period for all SAEs will begin after informed consent is obtained and end after procedures for the final study visit have been completed. Institution and Investigator understand and agree that Investigator and Institution are obligated under applicable law and regulations to report any serious and related adverse event, if any, that occurs during treatment with the Product to the Institution's IRB and to the governing regulatory authority in accordance with applicable filing timelines promptly after any such event occurs. Prior to or at the time of filing any such report with the governing regulatory authority, Investigator, within 24 hours of first knowledge of such serious and related adverse event, will also transmit an information copy of the report to Genzyme via fax, attention: Genzyme PV, [contact] or by e-mail to [contact]. In accordance with the standard operating procedures and policies of the local Institutional Review Board (IRB)/Independent Ethics Committee (IEC), the site investigator will report SAEs to the IRB/IEC.

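### Table 2 asks for confirmation by stopping or reducing a drug already injected, so Probably cannot be assigned and some likely related events have no grade

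*Combined protocol and SAP*

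**What the plan says.** Section 10 states that the relationship of an adverse event to Synvisc-One "should be assessed using the following the guidelines in Table 2". Table 2 has four grades.

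- *Definitely* opens with an alternative: "Previously known toxicity of agent; or an event that follows a reasonable temporal sequence from administration of the drug". The second alternative then adds a recognised or anticipated pattern of reaction and two further conditions: "that is confirmed by stopping or reducing the dosage of the drug; and that is not explained by any other reasonable hypothesis".
- *Probably* has no such alternative. It needs suitable timing, a recognised pattern, an event "that is confirmed by stopping or reducing the dosage of the drug", and little likelihood that the subject's condition or another intervention accounts for it.
- *Possibly* needs suitable timing and a recognised pattern, "but that could readily have been produced by a number of other factors".
- *Unrelated* needs certainty that there is no relationship.

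Section 7.1 says "All subjects in this study will receive the treatment", so the scale applies to the whole cohort. Section 7.4.1 gives the treatment as one 6 mL injection into the target knee at baseline, with retreatment possible no sooner than 4 months after the previous injection. Section 4.3 lists the local reactions already known: arthralgia, arthritis, arthropathy, injection site pain and joint effusion. Section 10.1.1 obliges the institution and investigator "to report any serious and related adverse event" to the IRB and the regulator, with a copy to the funder within 24 hours of first knowledge.

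**The concern.** Confirmation by stopping or reducing the dose is a dechallenge test. It suits a drug taken repeatedly, where dosing can be interrupted to see whether the event subsides. It does not suit a product that is already in the joint when the event appears.

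Safety of one or more injections is among the objectives in the synopsis. Sections 8.1.13 and 10 have the relation to study drug recorded for adverse events. If a grade cannot be reached, or an event has nowhere to go, the recorded relatedness depends on how each assessor works around the wording. Section 10.1.1 also makes some reporting depend on whether a serious event is related, and no section says which grades count as related.

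**Working it through.** No rate, sample size or power figure enters this point, and the plan gives no figure to reproduce. The check sets the conditions in each row of Table 2 against the treatment described in Section 7.4.1.

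**Step 1. Conditions by grade.**

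| Grade | Suitable timing | Recognised pattern | Dechallenge | Other causes |
|---|---|---|---|---|
| *Definitely*, route 1 (known toxicity) | not stated | not stated | no | not stated |
| *Definitely*, route 2 | yes | yes | **yes** | no other reasonable explanation |
| *Probably* | yes | yes | **yes** | other explanation unlikely |
| *Possibly* | yes | yes | no | other causes readily available |
| *Unrelated* | – | – | no | certainty of no relationship |

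The row for *Definitely* is loosely punctuated. The natural reading is that the later conditions qualify the second alternative only, so route 1 stands alone.

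**Step 2. Can the dechallenge be done?** An injection already given cannot be stopped or reduced. Section 11.1 allows study treatment to be discontinued after an adverse event, but withholding a later injection does not test whether an earlier one caused the event. *Probably* and *Definitely* route 2 therefore cannot be met: one of four grades, and one of two routes to another.

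**Step 3. Where do events go?**

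- *A. A reaction listed in Section 4.3.* Route 1 admits it to *Definitely* without dechallenge. Route 1 also has no timing or alternative-cause test of its own, so arthralgia in an osteoarthritic knee long after the injection could qualify on the wording alone.
- *B. Suitable timing and an anticipated pattern, but not a known toxicity and no ready alternative cause.* Route 2 and *Probably* fail on dechallenge alone. *Possibly* fails because it needs ready alternative causes. *Unrelated* fails because it needs certainty. No grade fits.
- *C. As B, but with a new pattern of reaction.* Route 2 and *Probably* now fail on both pattern and dechallenge, and *Possibly* on both pattern and alternative causes. No grade fits, and deleting the dechallenge clause alone would not help.
- *D. Suitable timing, anticipated pattern, ready alternative causes, and not a known toxicity.* *Possibly* fits.

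The gap is therefore B and C. The dechallenge clause decides B; C also needs the pattern condition relaxed.

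**Step 4. What follows from the grade?** Section 10.1.1 has all SAEs documented whether or not related, and Section 15.2 sends serious events to the IRB regardless of causality. The regulator report and the 24-hour copy to the funder are framed around events that are both serious and related. For B and C that trigger is undefined twice over: no grade fits, and no list says which grades qualify.

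**The case against.** The strongest reply is that this is a wording mismatch with little consequence.

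- Table 2 is introduced as guidelines, and nothing in the documents shows that investigators would apply the clause literally.
- The commonest related events are known reactions and have a route to *Definitely*.
- The IRB receives serious events whatever their cause, and Section 15.5 has adverse events reported to the Sponsor.
- Nothing excludes *Possibly* from related.
- Section 13 plans no analysis by relatedness grade; Section 4.3 says only that adverse reactions are captured and tabulated.

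Most of this stands, and it limits the point to a low priority. It does not remove it. Calling the table guidelines supplies no other rule, and no other section does. Route 1 covers only what is already known, whereas B and C are the events a safety evaluation most needs to classify.

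Three stronger readings are tempting but not supported:

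- *Device-related events will be misgraded, or will all collapse into Possibly.* Known reactions can go to *Definitely*, and a new reaction without a ready alternative cause does not meet *Possibly* either.
- *The number affected can be read from the synopsis.* It cites 4 of 77 subjects (4/77 = 5.2%) with device-related events after a second injection, and 0.052 × 150 = 7.8. That is not a count of misgraded events. Nothing says the 4 had unfamiliar reactions, follow-up was 4 weeks after re-injection, and only subjects who meet the retreatment criteria are re-injected here.
- *Serious events would go unreported.* Sections 10.1.1 and 15.2 rule this out for the IRB.

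**Conclusion.** The point holds in a limited form and is a minor one. As written, *Probably* can never be assigned, and *Definitely* can be reached only as an already-known toxicity. A likely related event that is neither a known toxicity nor readily explained otherwise has no grade, and may be misgraded or left ungraded. How many such events would arise cannot be derived from the documents. No efficacy endpoint is touched.

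The conclusion rests on two assumptions. First, the table is applied as worded. Second, treatment is the single injection of Section 7.4.1. Section 7.4.3 instead describes 2 mL given weekly for three injections, and Section 8.1.8 also refers to 2 mL; these sections must be reconciled with 7.4.1. Under a weekly course a remaining injection could be withheld, but one already given still could not be undone.

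**What to change.** In Table 2:

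1. In the *Definitely* and *Probably* rows, replace the stopping or reducing clause with criteria that can be judged after a completed injection: timing after the injection, absence of a better explanation, and recurrence after a later injection where one is given under the protocol. This asks for no injection to be given to settle causality.
2. Make a known reaction pattern supportive rather than required in the related grades, so that a new injection-linked event has a grade.
3. State whether the timing and alternative-cause criteria also apply to known toxicities.

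In Section 10.1.1 and for tabulation, state that *Definitely*, *Probably* and *Possibly* all count as related.

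The cost is table wording and CRF guidance, with possibly a few more events classed as related. Treatment, visits, sample size and endpoints do not change.

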10.1.1 Serious Adverse Experience Reporting

Study sites will document all SAEs that occur (whether or not related to study drug) per [UCSF CHR Guidelines](#). The collection period for all SAEs will begin after informed consent is obtained and end after procedures for the final study visit have been completed. Institution and Investigator understand and agree that Investigator and Institution are obligated under applicable law and regulations to report any serious and related adverse event, if any, that occurs during treatment with the Product to the Institution's IRB and to the governing regulatory authority in accordance with applicable filing timelines promptly after any such event occurs. Prior to or at the time of filing any such report with the governing regulatory authority, Investigator, within 24 hours of first knowledge of such serious and related adverse event, will also transmit an information copy of the report to Genzyme via fax, attention: Genzyme PV, [contact] or by e-mail to [contact]. In accordance with the standard operating procedures and policies of the local Institutional Review Board (IRB)/Independent Ethics Committee (IEC), the site investigator will report SAEs to the IRB/IEC.

11 DISCONTINUATION AND REPLACEMENT OF SUBJECTS

11.1 Early Discontinuation of Study Drug

A subject may be discontinued from study treatment at any time if the subject, the investigator, or the Sponsor feels that it is not in the subject's best interest to continue. The following is a list of possible reasons for study treatment discontinuation:

- Subject withdrawal of consent (or assent)
- Subject is not compliant with study procedures
- Adverse event that in the opinion of the investigator would be in the best interest of the subject to discontinue study treatment

- Protocol violation requiring discontinuation of study treatment
- Lost to follow-up
- Sponsor request for early termination of study
- Positive pregnancy test (females)

If a subject is withdrawn from treatment due to an adverse event, the subject will be followed and treated by the Investigator until the abnormal parameter or symptom has resolved or stabilized.

All subjects who discontinue study treatment should come in for an early discontinuation visit as soon as possible and then should be encouraged to complete all remaining scheduled visits and procedures.

All subjects are free to withdraw from participation at any time, for any reason, specified or unspecified, and without prejudice.

Reasonable attempts will be made by the investigator to provide a reason for subject withdrawals. The reason for the subject's withdrawal from the study will be specified in the subject's source documents.

11.2 Withdrawal of Subjects from the Study

A subject may be withdrawn from the study at any time if the subject, the investigator, or the Sponsor feels that it is not in the subject's best interest to continue.

All subjects are free to withdraw from participation at any time, for any reason, specified or unspecified, and without prejudice.

Reasonable attempts will be made by the investigator to provide a reason for subject withdrawals. The reason for the subject's withdrawal from the study will be specified in the subject's source documents.

11.3 Replacement of Subjects

Subjects who withdraw from the study treatment in the first 6 months of the study will be replaced. Replacement injected will be requested from Genzyme based on need.

12 PROTOCOL VIOLATIONS

A protocol violation occurs when the subject, manufacturer, or investigator fails to adhere to significant protocol requirements affecting the inclusion, exclusion, subject safety and primary endpoint criteria. Protocol violations for this study include, but are not limited to, the following:

- Failure to meet inclusion/exclusion criteria
- Use of a prohibited concomitant medication

Failure to comply with Good Clinical Practice (GCP) guidelines will also result in a protocol violation. [name] will determine if a protocol violation will result in withdrawal of a subject.

When a protocol violation occurs, it will be discussed with the investigator and a Protocol Violation Form detailing the violation will be generated. This form will be signed by a Sponsor representative and the Investigator. A copy of the form will be filed in the site's regulatory binder and in the Sponsor's files.

13 STATISTICAL METHODS AND CONSIDERATIONS

Prior to the analysis of the final study data, a detailed Statistical Analysis Plan (SAP) will be written describing all analyses that will be performed. The SAP will contain any modifications to the analysis plan described below.

Data Sets Analyzed

The primary endpoint is based on a responder analysis. Response is defined as maintaining a Worst Knee Pain score ≤ 3 on a 0-10 pain scale throughout the 6 months following the baseline injection. Trial success will be based on a non-inferiority test (with 20% non-inferiority threshold) of this response rate in comparison to an external criterion of 70% (Bellamy 2010). Secondary endpoints include determining the duration of response after subsequent injection, determining the effects of treatment on activity levels and quality of life, and describing the three-year time course of each of the study endpoints. The sample size will be $n=150$ subjects followed for up to 3 years after baseline injection. The power to conclude non-inferiority for a true response rate of 65% is better than 92%.

Demographic and Baseline Characteristics

The following demographic variables at screening will be summarized by: race, gender, age, height and weight.

Analysis of Primary Endpoint

The primary endpoint for the study will be analyzed using a responder analysis. The proportion of responders following injection within the 6 months following the baseline injection will be calculated based on Worst Knee Pain scores ≤ 3 on a 0-10 pain scale, which is a threshold consistent with other similar studies (Tubach 2005, Bellamy 2010). The primary endpoint is defined as non-inferiority (with 20% non-inferiority threshold) of the proportion of responders in our study relative to an external criterion of 70% for the responder proportion (Bellamy 2010).

Primary Statistical Analysis: Define the true probability of a subject being a responder as π and the non-inferiority threshold $\delta_{NI} = 0.20$. We require the test of

$$H_0: \pi < 0.70 - \delta_{NI} = 0.50$$

vs. the alternative

$$H_1: \pi \geq 0.70 - \delta_{NI} = 0.50.$$

Non-inferiority will be accepted if the null hypothesis can be rejected with a 2.5% one-sided type I error. To test this hypothesis, we will use the Wilson-Agresti method for a single binomial proportion. Non inferiority will be accepted if the 95% Wilson-Agresti (REF BROWN ET AL 2001) interval for the proportion of responders excludes the null rate of 0.50.

Missing Data:For the analysis of the percentages of positive responders, patients who discontinue the study prior to the Week 26 assessment due to either target knee-related AEs or due to lack of efficacy will be classified as non-responders in the efficacy analysis. Patients who discontinue the study for other reasons will have the responder status imputed using the last observation carried forward (LOCF) method.

Operating Characteristics

The following table shows the power to accept non-inferiority for two assumptions on sample size (n=150 and a smaller sample size reflecting potential dropout of n=120):

| True Responder Rate (□. | Sample Size n=150 | Sample Size n=120 |
|----------------------------|----------------------|----------------------|
| 0.60 | 72% | 61% |
| 0.65 | 97% | 92% |
| 0.70 | >99% | >99% |
| 0.75 | >99% | >99% |

Table 1. Power to conclude non-inferiority for variety of true responder rates and two values for sample size.

Thus, even after conservatively accounting for subject dropout, we will be well-powered to conclude non-inferiority if the true responder rate is at least 65%.

Secondary Outcomes:

- **Duration of response to subsequent injections:** Though symptoms can be improved for periods up to 6 months, pain symptoms can recur in which case patients will receive a subsequent injection. The duration of these repeated treatments of hylan G-F 20 will be studied.

- **Effect of treatment on activity levels and quality of life:** The effects of treatment with hylan G-F 20 on activity levels (using objective activity measures utilizing accelerometer

and Physical Activity Enjoyment Scale) and quality of life scores (WOMAC, SF-12) comparing baseline to treatment at 3 months.

- **Three year follow up:** Patients will be followed for up to three years. We will examine the time courses of pain score, activity level, and quality of life over the entire three year span.

Analysis of Secondary Endpoints

Secondary Analyses: Secondary endpoints will be analyzed using confidence intervals as no specific hypothesis tests are being conducted.

The following secondary analyses will be conducted:

- **Duration of response:** Using Kaplan-Meier survival analysis techniques, we will estimate the probability of duration of response over time curve (survival curve) and its confidence limits and also the median duration time and confidence interval. Duration of response analyses will be conducted for the initial injection and also in the subset of patients that receive a follow-up injection.

- **Activity levels and quality of life:** We will estimate the average change and corresponding confidence limits from baseline to 3 months in each of the activity level measures (accelerometer test, walk test, Physical Activity Enjoyment Scale) and the quality of life measures (WOMAC, SF-12). The confidence intervals will be constructed using one sample t-distributions; in the event of strongly skewed measures, we will either use bootstrapping or transformation to construct more accurate intervals. The average change and the endpoints of the confidence intervals can be referenced to external clinically important improvements for comparison.

- **Long term outcome:** We will examine the time course for the pain score, activity level, and quality of life measures across the three years of the study. Estimates and confidence intervals will be derived using mixed effects linear models. Specifically, for each longitudinal outcome measure, we will model it as a function of the (categorical) time point. Intrasubject correlation will be accommodated by either a compound symmetry, autoregressive, or general covariance structure depending on best fit according to BIC. In the event of very non-normally distributed outcomes, we will employ normalizing transformations prior to the analysis. These analyses will be conducted using the Mixed procedure in SAS.

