| 
STATISTICS Secondary Endpoints
 | 
For subsequent injections, duration of response over time and median duration of response will be estimated using survival analysis techniques. Inference for activity levels and quality of life will focus on changes from baseline to 3 months. We will examine the time course for the longitudinal data on pain score, activity level, and quality of life measures across the three years of the study using mixed effects models.
 |
| 
Rationale for Number of Subjects
 | 
Power Calculation
 
Bellamy demonstrated in his paper from 2007 (table 3) that a BLISS response at any time during the study was achieved in 70% receiving appropriate care and Hylan G-F 20 and only in 38% of patients receiving appropriate care ($P < 0.0001$). A power calculation using a one-sample comparison of proportion with hypothesized value sample size was performed to determine non-inferiority to the 70% results quoted by Bellamy. Power calculations were measured using STATA's SAMPSI calculator. If we postulate a 20% non-inferiority limit (i.e. that at least 50% of patients receiving G-F 20 will achieve a BLISS response), the sample size required to have 90% power and
 |

| | |
|------------------------------------|--|
| | 
$\alpha=0.025$ to show non-inferiority at 50% would be 70. For a 10% non-inferiority limit with 90% power and $\alpha=0.025$, the required sample size is 274, and for 15% non-inferiority limit with 90% power and $\alpha=0.025$, it is 124 patients. These numbers do not allow for dropouts, therefore, we intend to recruit 150 subjects to account for dropout.
 
Conservatively assuming a 20% rate of drop-out, the resulting sample size of $n=120$ has better than 90% power (one sided test with $\alpha=0.025$) to show non-inferiority assuming the true responder rate is 65% (i.e. not quite as high as the 70% external reference).
 |
| 
DATA MANAGEMENT PLAN
 | 
Data management and analysis for the study will be performed by the Biostatistics Consulting Unit (BCU) of UCSF’s Clinical and Translational Science Institute (CTSI). Data will be stored on a HIPAA-compliant server. The server room has state-of-the-art environmental controls and security features and is protected by a firewall and anti-virus software.
 |

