13.6 Sample Size and Randomization

Bellamy demonstrated in his paper from 2007 (table 3) that a BLISS response at any time during the study was achieved in 70% receiving appropriate care and Hylan G-F 20 and only in 38% of patients receiving appropriate care ($P < 0.0001$). A power calculation using a one-sample comparison of proportion with hypothesized value sample size was performed to determine non-inferiority to the 70% results quoted by Bellamy. Power calculations were measured using STATA's SAMPSI calculator. If we postulate a 20% non-inferiority limit (i.e. that at least 50% of patients receiving G-F 20 will achieve a BLISS response), the sample size required to have 90% power and $\alpha = 0.025$ to show non-inferiority at 50% would be 70. For a 10% non-inferiority limit with 90% power and $\alpha = 0.025$, the required sample size is 274, and for 15% non-inferiority limit with 90% power and $\alpha = 0.025$, it is 124 patients. These numbers do not allow for dropouts, therefore, we intend to recruit 150 subjects to account for dropout.

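### Primary response is defined as sustained over 6 months, but its 0.50 success threshold and 65–70% planning rates come from an any-time BLISS response

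*Combined protocol and SAP*

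**What the plan says.** The only explicit responder rule is in section 13 under Data Sets Analyzed: "Response is defined as maintaining a Worst Knee Pain score ≤ 3 on a 0-10 pain scale throughout the 6 months" following the baseline injection. The next sentence ties success to it: "Trial success will be based on a non-inferiority test (with 20% non-inferiority threshold) of this response rate", compared with an external 70%. The hypotheses under Analysis of Primary Endpoint then set the null rate at 0.70 − 0.20 = 0.50, with a one-sided 2.5% test.

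The 70% is described in the synopsis (Primary Analysis Endpoint and Rationale for Number of Subjects) and in section 13.6: "a BLISS response at any time during the study was achieved in 70% receiving appropriate care and Hylan G-F 20". The sample size rationale in the synopsis and section 13.6 also gives the meaning of the 50% limit: "at least 50% of patients receiving G-F 20 will achieve a BLISS response".

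Elsewhere the endpoint is worded more loosely. Analysis of Primary Endpoint in section 13 says: "The proportion of responders following injection within the 6 months following the baseline injection will be calculated based on Worst Knee Pain scores", with the cut-off ≤ 3. The synopsis has nearly the same sentence, and section 4.1 has it without the cut-off. Section 4.1 also lists two co-primary endpoints based on PASS over 36 months, which section 13 does not analyse.

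On power, Operating Characteristics in section 13 concludes that "we will be well-powered to conclude non-inferiority if the true responder rate is at least 65" per cent.

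**The concern.** The tested endpoint and its benchmark follow different time rules. A subject who is at or below 3 at every assessment is also at or below 3 at some assessment. On a common measure and schedule, the sustained rate is therefore at most the any-time rate, and usually lower. A margin of 20 points below an any-time rate does not say what sustained rate would be acceptably close to the reference treatment. The planning rates of 65% and 70% are likewise placed around an any-time figure.

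The measures differ as well: BLISS in the reference, Worst Knee Pain ≤ 3 here. Nothing in the plan shows that the two are comparable, so even the direction of the gap from the external 70% cannot be fixed from the documents.

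The looser wording adds to the problem. It does not say whether any, every or the last assessment counts. In an open-label, single-arm trial, that leaves room to adopt the easier reading once the data are known.

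**Working it through.** **Inputs from the plan.** Null rate 0.50; 95% Wilson-type interval that must exclude it; n = 150 planned and n = 120 after 20% dropout; reference rate 0.70; planning rate 0.65. Worst Knee Pain is listed in section 9 at the contacts at weeks 6, 12 and 18 and at the month 6 visit.

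**Inputs assumed.** The plan gives no any-time rate for Worst Knee Pain ≤ 3 and no share of any-time responders who stay ≤ 3 (retention). Both are varied below.

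**Step 1: cut-offs.** The smallest count x whose 95% Wilson lower limit exceeds 0.50 is 88 of 150 (lower limit 0.507) and 71 of 120 (lower limit 0.502). The Agresti-Coull interval gives the same counts.

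**Step 2: the plan's own power.** P(X ≥ 71 | n = 120, p) is 61.2% at p = 0.60, 92.3% at 0.65 and 99.6% at 0.70. These match the stated 61%, 92% and >99%. The arithmetic is sound given the true rate; the question is where that rate comes from.

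**Step 3: retention, with the any-time rate set at 0.70.** Sustained rate = 0.70 × retention. Chance of success = P(X ≥ 88 | 150) or P(X ≥ 71 | 120).

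| Retention | Sustained rate | n = 150 | n = 120 |
|---|---|---|---|
| 100% | 0.70 | 99.9% | 99.6% |
| 90% | 0.63 | 88% | 83% |
| 85% | 0.595 | 62% | 57% |
| 80% | 0.56 | 28% | 27% |
| 71% | 0.50 | 2% | 3% |

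For the sustained rate to equal the planning value of 0.65, retention would have to be 0.65 / 0.70 = 93%.

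**Step 4: any-time rate, with retention set at 80% and n = 150.**

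| Any-time rate | Sustained rate | Chance of success |
|---|---|---|
| 0.60 | 0.48 | 0.6% |
| 0.70 | 0.56 | 28% |
| 0.80 | 0.64 | 92% |
| 0.85 | 0.68 | 99% |

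**Step 5: one dataset, two conclusions.** Suppose 105 of 150 subjects (70%) reach ≤ 3 at some assessment. Counted as any-time responders, 105 ≥ 88 and the trial succeeds. If 18 of the 105 (17%) do not hold ≤ 3, the sustained count is 105 − 18 = 87, one short of 88, and the trial fails.

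**The case against.** The strongest reply is that the sustained rule is the harder one, so testing it against 0.50 is conservative. That stands: a reader might infer inflated false positives from the mismatch, but for the sustained endpoint there is none. The power table is also explicitly conditional on the true rate, so it is not false. What remains is that neither the threshold nor the rates called plausible were derived for this endpoint.

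A second reply is that the looser phrase merely names the observation window, and that the sustained rule governs. That is a fair reading, and the phrase should not be called a rival definition. It still fails to state the rule in the places where the endpoint is presented as primary.

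A reader might go further and infer a separate Week 26 endpoint. The documents do not support that. Week 26 appears only in the missing-data rule for "patients who discontinue the study prior to the Week 26 assessment due to either target knee-related AEs or due to lack of efficacy"; counting those patients as non-responders is compatible with a sustained rule, and their classification is already settled.

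A reader might also infer from Appendix 1 that Worst Knee Pain is measured only once after injection within the window. But that table has no column for any email or phone contact, and section 9 lists the score at those contacts.

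Finally, section 13 promises a detailed SAP before final analysis, which may modify the plan. Nothing can be said about its content, and the promise does not resolve the mismatch in the present text.

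**Conclusion.** Wrong as written. The success threshold of 0.50 and the 65–70% planning rates are unsupported for the sustained response that section 13 defines, because they rest on an any-time response on another measure and the plan makes no adjustment or comparability argument.

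The size is a sensitivity range, not an expected loss. At an any-time rate of 0.70 and n = 150, the chance of success runs from 99.9% at full retention to 2% at 71% retention. At 80% retention it runs from 0.6% to 99% as the any-time rate goes from 0.60 to 0.85. A reader might conclude that the trial is underpowered; the documents do not show that, since they give neither quantity. They show only that the stated power has no basis for this endpoint.

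**What to change.** State one responder rule, identically in the synopsis, section 4.1 and section 13, and name the Worst Knee Pain assessments that count (section 9: weeks 6, 12 and 18 and month 6). Then choose one of two routes.

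- **(a)** Make response at any of those assessments primary, which matches the time rule of the 70%. Justify comparability with BLISS, and report sustained response as a secondary proportion with a confidence interval. Cost: the sustained claim becomes secondary.
- **(b)** Keep sustained response as primary and restate the benchmark, margin and planned power for it, without implying that the 70% supports them. Cost: the stated power may be less favourable.

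Under either route:

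- State how the analysis treats scores recorded after a second injection inside the 6-month window. The synopsis and sections 3.1 and 7.4.1 allow retreatment from 4 months, so under (a) in particular such a score could be credited to the baseline injection.
- For patients who leave for other reasons and "will have the responder status imputed using the last observation carried forward (LOCF) method", state whether one early score carried forward can count as a response over the whole 6 months.
- Reconcile the 36-month PASS co-primary endpoints in section 4.1 with section 13.
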